5.4.2. Additional considerations

5.4.2.1. Analysis of solicited events

The analysis of solicited events will be performed on Solicited Safety Set. The intensity of the following solicited events will be assessed as described:

Table 9 Intensity scales for solicited symptoms in adults

Adults		
Event	Intensity grade	Parameter
Pain at administration site	0	None
	1	Mild: Any pain neither interfering with nor preventing normal every day activities.
	2	Moderate: Painful when limb is moved and interferes with every day activities.
	3	Severe: Significant pain at rest. Prevents normal every day activities.
Redness at administration site		Record greatest surface diameter in mm
Swelling at administration site		Record greatest surface diameter in mm
Temperature*		Record temperature in °C/°F with 1 decimal Temperature will be analysed in 0.5°C increments from ≥ 38.0°C /100.4°F) Grade 3 fever is defined as > 39.0°C /102.2°F
Headache	0	Normal
Fatigue		
Nausea	1	Mild: Easily tolerated
Vomiting	2	Moderate: Interferes with normal activity
Diarrhea	3	Severe: Prevents normal activity
Abdominal pain		

* Preferred location for measurement will be the oral cavity. "Fever" = temperature ≥38.0°C/100.4°F regardless of the location of measurement.

The maximum intensity of local injection site (redness and swelling) will be scored at GSK Biologicals as follows:

0:	≤ 20 mm
1:	> 20 mm to ≤50 mm
2:	> 50 mm to ≤100 mm
3:	>100 mm

Duration in days of solicited administration site and systemic events within 7 days after vaccination will be tabulated by study group and overall, and if needed by age group. The derivation rule of duration in days for solicited events is detailed in section 10.1.2.11.

5.4.2.2. Exclusion of implausible solicited Event

Some local and systemic events will be directly measured by the participant and cannot be changed even if they are biologically implausible. Therefore, these implausible measurements will be removed from the analysis but included in listings. Implausible measurements are summarized in the table below:

Table 10 Implausible Solicited Events

Parameter	Implausible measurements
Body temperature	≤ 33°C or ≥ 42°C
Erythema	Measurements < 0 mm For participants ≥ 6 years: ≥ 900 mm
Swelling	Measurements < 0 mm For participants ≥ 6 years: ≥ 500 mm

5.4.2.3. Analysis of Unsolicited Adverse Events

The analysis of unsolicited events will be performed on ES

5.4.2.4. Combined Solicited and Unsolicited Adverse Events

The combined analysis of solicited and unsolicited events will be performed on ES. A summary of participants with all combined solicited and unsolicited adverse events will be provided.

Solicited adverse events will be coded by MedDRA.

For clintrial.gov and EudraCT posting purposes, a summary of combined solicited and unsolicited adverse events will be produced by System Organ Class and preferred terms and according to occurrence of each event.

5.4.2.5. Other analysis

Other safety analysis will be performed on ES.

Concomitant medications will be coded using the GSKDRUG dictionary. The number and percentage of maternal participants taking concomitant medications (any medication, any antipyretic and any antipyretic taken prophylactically, respectively) within 7 days

following vaccination, 30 days following vaccination, up to 6 weeks post-delivery and up to 6 months post-delivery will be summarized by group. A listing will also be provided.

The number and percentage of infants taking previous and concomitant medications/vaccinations from birth up to 6 weeks after birth, 6 months after birth and 1 year after birth will be summarized by group. A listing will also be provided.

6. ANALYSIS INTERPRETATION

All comparative analyses will be descriptive with the aim to characterize the difference in immunogenicity between groups. These descriptive analyses should be interpreted with caution considering that there is no adjustment for multiplicity for most of these comparisons.

7. CONDUCT OF ANALYSES

7.1. Sequence of analyses

An interim analysis of safety endpoints for both maternal and infant participants has been performed, with the focus on demonstrating the safety profile at Day 43 post-delivery. The interim analysis was deemed necessary following the identification of the safety signals documented in protocol amendment 4, which assisted in the better characterization of the safety information including the signals. The interim analysis was performed after all infants completed the 43 days post-delivery timepoint. The safety endpoints are identical to those listed in section 2, and the statistical analysis methods are similar to section 5.4.1. with minor modifications. In addition, summaries of demographics, participant disposition, concomitant medication/vaccinations and medical history was included. This analysis was performed by an external Independent Data Analysis Center (IDAC). In addition, monthly safety analyses are conducted, where most of the analyses have been generated by IDAC and monitored by the SRT on a monthly basis and by an Independent Data Monitoring Committee (IDMC) on a bi-monthly basis. Additional non-standardized ad-hoc analyses (safety signal deep dive) are performed by internal GSK.

6 Month Post-delivery interim analysis occurred as described below:

- When all maternal and infant participants enrolled completed 6 months follow-up post-delivery/birth (to evaluate primary and secondary efficacy endpoints, reactogenicity and safety)

Final analysis will occur as described below:

- When all infant participants have completed Visit 5-NB (month 12, LSLV), a final safety analysis (for all maternal and infant participants in both Stage A and Stage B), a final secondary efficacy analysis up to 12 months follow up post birth, and a final immunogenicity analysis will be performed. Analyses of any evaluated tertiary endpoints may also be performed.

6 Month Post-delivery interim analysis was performed by internal GSK, so will be the final analysis.

If the data for tertiary endpoints becomes available at a later stage, (an) additional analysis/analyses will be performed.

Description	Disclosure Purpose
Day 43 post-delivery interim analysis	Internal
6 Month post-delivery interim analysis	Public Disclosure.
Final Analysis at Month 12 post birth	Public Disclosure, Study Report

7.2. Statistical considerations for interim analyses

Not applicable.

8. CHANGES FROM PLANNED ANALYSES

- By-participant listings of SAEs, AEs leading to study withdrawal, MAEs, adverse pregnancy outcomes and pregnancy related AESIs will be prepared and released. Such listings have already been released in earlier analyses. Due to study enrolment/vaccination stop, the study has been unblinded already before the final analysis.
- A sensitivity analysis for immunogenicity results excluding participants from Bangladesh, for which HIV testing was not performed before their enrollment into the study, has been added.
- Between group evaluations for immunogenicity analysis was clarified to be performed among RSV MAT and Control instead of vaccination groups, the wording has been corrected.
- In February 2022, enrollment and vaccination were stopped because of an imbalance in preterm births and associated neonatal deaths observed between the RSVPreF3-Mat and placebo groups. Subsequently the study was unblinded, and therefore the presented VE endpoints are descriptive.
- Subgroup analyses by economic region (LMIC and HIC) will be performed for demography, efficacy, and safety evaluations.
- Subgroup analyses by gestational age at birth will be performed for demography and safety evaluations.
- Sensitivity analysis for primary efficacy endpoints by using a negative binominal regression model have been removed.

9. NON-STANDARD DATA DERIVATION RULES AND STATISTICAL METHODS

The following sections describe additional derivation rules and statistical methods which are not presented in section 10.1.

9.1. Gestational age at vaccination

Gestational age at vaccination in weeks for maternal participants will be entered by the investigator and used for our analyses. It will not be derived from the estimated date of delivery.

9.2. Immunogenicity

For a given participant and given immunogenicity measurement, missing or non-evaluable measurements will not be replaced. Therefore, an analysis will exclude participants with missing or non-evaluable measurements.

- For the within-group assessment, the descriptive analysis performed for each assay at each timepoint will exclude participants with a missing or non-evaluable measurement.
- For the between group assessments, statistical model will be fitted based on the participants having a result at both the baseline and the considered timepoint.

The GMT/GMC and its 95% CI will be obtained by exponentiating the mean and its 95% CI of the log-transformed titres/concentrations. All CI computed will be two-sided 95% CI.

Placental transfer is defined as the ratio of RSVPreF3 IgG-specific antibody concentrations between cord blood (or blood sample from infants collected within 3 days after birth if cord blood is not available) and maternal blood sample at delivery (or within 3 days after delivery if blood sample is not collected during delivery).

9.2.1. Assay cut-offs

9.2.1.1. Assay cut-offs for serology results

A seronegative participant is a participant whose antibody titre is below the cut-off value of the assay. A seropositive participant is a participant whose antibody titre is greater than or equal to the cut-off value of the assay. The cut-off tests for immunogenicity evaluation will be as per following:

System	Component	Method	Unit	Cut-off (LLOQ)	ULOQ
Serum	RSV-A Neutralising Antibody	CCI			
Serum	RSVPreF3 IgG antibody concentrations				
Serum	RSV-B Neutralising Antibody*				

Note: the assay cut-off (LLOQ), ULOQ and units may be further adjusted at time of analysis.

*: RSV-B neutralizing antibody titers will no longer be assessed as part of the secondary immunogenicity endpoints.

9.2.1.1.1. Assay cut-offs for central nasal swabs

System	Component	Method	Unit	Cut-off
Nasal Swab	RSV-A positive	CCI		
Nasal Swab	RSV-B positive			

9.2.2. RTI and LRTI

Cases will be classified (during data analyses) according to the definitions that follow.

Table 11 MA-RTI case definitions for data analysis in maternal participants

RSV-MA-RTI	Medically attended visit for RTI symptoms AND Confirmed RSV infection ^{1,2}
RSV hospitalization	Confirmed RSV infection AND Hospitalized for acute medical condition ³
All-cause MA- RTI	Medically attended visit for RTI symptoms

¹ Confirmed RSV infection defined in Section 4.2.6.3 of the Protocol

² RSV (nasal swab) sampling and testing as specified in Table 14 of the Protocol.

³ Hospitalization is defined as admission for observation or treatment based on the judgement of a health care provider.

MA-RTI = Maternal, medically attended respiratory tract illness

Table 12 RTI/LRTI case definitions for data analysis in infants

RSV-RTI	Runny nose, OR Blocked nose, OR Cough AND Confirmed RSV infection ^{4,5}
RSV-LRTI	History of cough OR difficulty in breathing ¹ AND SpO ₂ < 95% ² , OR RR increase ³ AND Confirmed RSV infection ^{4,5}
RSV-severe LRTI	Meeting the case definition of RSV-LRTI AND SpO ₂ < 93% ² , OR lower chest wall in-drawing OR inability to feed OR failure to respond/unconscious
RSV hospitalization	Confirmed RSV infection ^{4,5} AND Hospitalized for acute medical condition ⁶
All-cause RTI	Runny nose, OR Blocked nose, OR Cough
All-cause LRTI	History of cough OR difficulty in breathing ¹ AND SpO ₂ < 95% ² , OR RR increase ³
All-cause LRTI hospitalization	Hospitalized due to all cause LRTI as defined above

Definitions based on [Modjarrad, 2016]; except that definitions for severe and very severe RSV LRTI have been merged. **RTI** = respiratory tract illness; **LRTI** = lower respiratory tract illness; **RR** = respiratory rate; **SpO₂** = blood oxygen saturation by pulse oximetry.

¹ Based on history reported by parents/LARs and includes difficulty in breathing (e.g. showing signs of wheezing or stridor, tachypnoea, flaring [of nostrils], chest in-drawing, apnea).

² For blood oxygen saturation (SpO₂), the lowest value monitored will be used. In high altitudes (>2500m), SpO₂ <92% for LRTI, <90% for severe LRTI.

³ RR increase defined as:

- > 60/minute (< 2 months of age)
- > 50/minute (2 to < 12 months of age)
- > 40/minute (12 to 24 months of age)

⁴ Confirmed RSV infection

⁵ RSV (nasal swab) sampling and testing

⁶ Hospitalization is defined as admission for observation or treatment based on the judgement of a health care provider.

For RSV infection the sponsor will analyse nasal swabs by quantitative reverse transcription polymerase chain reaction (qRT-PCR) for the presence of RSV A/B. A positive (RSV A or B) test result constitutes a case of RSV infection.

In the event the collection of a nasal swab for testing by the sponsor is impossible, results from locally collected samples, tested with locally approved tests, may also be considered for the determination of a case of RSV infection.

For the analysis of RTI episode, a new RTI episode will be defined as any occurrence of cough and/or difficulty in breathing with an interval of at least 7 consecutive days without cough and/or difficulty in breathing since the last/previous episode of RTI.

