**8.4.6. Follow-up of infant respiratory tract illnesses**

Any infant RTI documented as ongoing at a previous visit/contact will be reviewed at subsequent visits/contacts during the surveillance interval until (a) all symptoms have resolved (except runny nose, often chronic in infants), or (b) the participant completes Visit 5-NB or (c) the participant is lost to follow up.

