5.2. Efficacy

5.2.1. Analysis of primary efficacy endpoints planned in the protocol

The primary analysis of vaccine efficacy (VE) will be based on the modified Full Analysis - Efficacy set for infants (modified FAS-E). A secondary analysis based on the Full Analysis – Efficacy set (FAS-E) and the Per Protocol - Efficacy set for infants will be performed to complement the modified FAS-E analysis.

Primary Efficacy Endpoints – Infant participants	Statistical Analysis Methods

From birth to 6 months, occurrences of medically assessed, RSV-associated severe LRTIs according to the case definitions.
 
OR
 
From birth to 6 months, occurrences of any medically assessed, RSV-associated LRTIs according to the case definitions.
	
CCI
 

CCI
 	

CCI

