5.4. Analysis of safety and reactogenicity

5.4.1. Analysis of safety and reactogenicity planned in the protocol

Safety analyses in **maternal participants** will include summaries by study group and age category (18-34, 35-39, ≥ 40 years of age; overall) of solicited administration site and systemic events (for stage A subjects), unsolicited AEs, MAEs, SAEs, MA-RTIs (RSV-associated MA-RTIs and all-cause MA-RTIs), AEs leading to study withdrawal, pregnancy outcomes and pregnancy related AESIs.

Safety analyses in **infant participants** will include summaries by study group, overall and gestational age at birth (≥ 37 weeks or < 37 weeks) of neonatal AESIs, MAEs, SAEs, AEs leading to study withdrawal, and the occurrence of RSV-associated RTIs, LRTIs, severe LRTIs, RSV-associated hospitalizations, all-cause RTI and all-cause LRTI.

Safety analyses for maternal participants and infants may also be reported by economic region (LMIC and HIC).

Analyses of solicited AEs will be performed on the Solicited Safety set (maternal participants only). Analyses of unsolicited AEs will be performed on the ES.

Primary Safety Endpoints – Infant Participants	Statistical Analysis Methods

Occurrence of SAEs, AEs leading to study termination and medically attended AEs from birth up to 6 months after birth
 
Occurrence of SAEs, AEs leading to study termination and medically attended AEs from birth up to 12 months after birth.
	
CCI

Secondary Safety Endpoints – Maternal Participants	Statistical Analysis Methods

Occurrence of solicited injection site and systemic events in Stage A participants during a 7-day follow-up period after vaccination (i.e. the day of vaccination and 6 subsequent days).
	
CCI

Occurrence of unsolicited adverse events (AEs) in all maternal participants during a 30-day follow-up period after vaccination (i.e. the day of vaccination and 29 subsequent days).
	

	CCI

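### The SAP's new-episode rule for RTI uses the LRTI entry symptoms and contradicts the RTI case definition in the same section, so RTI summaries counted by episode would not follow Table 12

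*SAP*

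**What the plan says.** Protocol section 9.4.6.2 leaves the rules for counting MA-RTI and RTI cases to the SAP. The only visible rule is one sentence at the end of the case-definition text in SAP section 9.2.2. Its first part sets the opening symptoms: "a new RTI episode will be defined as any occurrence of cough and/or difficulty in breathing". Its second part sets the gap that must come before a further episode can be counted: "with an interval of at least 7 consecutive days without cough and/or difficulty in breathing since the last/previous episode of RTI". Nasal symptoms appear in neither part. The sentence is not limited to infants, and it does not name the outputs it serves.

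Table 12, in the same section, gives the infant case definitions. RSV-RTI is "Runny nose, OR Blocked nose, OR Cough AND Confirmed RSV infection". All-cause RTI is the same symptom list without the RSV result, and difficulty in breathing is on neither list. RSV-LRTI and all-cause LRTI start instead from "History of cough OR difficulty in breathing", to which an oxygen-saturation or respiratory-rate criterion is added.

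SAP section 5.4.1 plans infant safety summaries by study group, overall and by gestational age at birth, covering "the occurrence of RSV-associated RTIs, LRTIs, severe LRTIs, RSV-associated hospitalizations, all-cause RTI and all-cause LRTI".

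On follow-up, Protocol section 8.4.6 has an ongoing infant RTI reviewed until "all symptoms have resolved (except runny nose, often chronic in infants"), or until the infant completes Visit 5-NB or is lost to follow-up.

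**The concern.** Two symptom lists are used for the same term within one section, and the SAP gives no reason. A programmer who derives episodes from the sentence and classifies illnesses from Table 12 will meet illnesses that are RTIs but belong to no episode, and episodes that are not RTIs. A programmer who starts from Table 12 will produce different episode counts.

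At stake is whether the by-group summaries of RSV-RTI and all-cause RTI follow the SAP's own case definition, and whether two people working from the SAP would reproduce each other's tables.

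**Working it through.** The documents state no sample size, event count or symptom frequency on this point, so there is no plan figure to reproduce. The check is logical.

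**Inputs (SAP section 9.2.2).** Four symptoms: runny nose, blocked nose, cough, difficulty in breathing.
- RTI definition (Table 12): runny or blocked or cough.
- LRTI entry symptoms (Table 12): cough or difficulty in breathing.
- Episode rule: cough or difficulty in breathing, after at least 7 consecutive days without them.

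**Step 1: symptom combinations.** There are 2^4 − 1 = 15 non-empty combinations.
- RTI definition met: all except difficulty in breathing alone, 15 − 1 = 14.
- Episode rule met: all except runny alone, blocked alone, and runny plus blocked, 15 − 3 = 12.
- Both met: 15 − 1 − 3 = 11.
- RTI but no episode: 14 − 11 = 3. Episode but no RTI: 12 − 11 = 1. Total disagreement: 4 of 15.
- LRTI entry symptoms against the rule: the same 12 combinations, so 0 of 15 disagree.

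These are counts of patterns. They are not rates expected in the trial.

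**Step 2: assumed timelines.** A new episode needs (first day of the new run) − (last day of the previous run) − 1 ≥ 7.

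| Assumed illness course | Episodes from Table 12 RTI symptoms | Episodes from the SAP rule |
|---|---|---|
| A. Runny days 1–5, blocked days 20–24 | 2 (gap 20 − 5 − 1 = 14) | 0 |
| B. Cough days 1–5, runny days 6–14, cough days 15–18 | 1 (no free day) | 2 (gap 15 − 5 − 1 = 9) |
| C. Cough days 1–5, difficulty in breathing only days 20–22 | 1 | 2 (gap 14) |
| D. Cough days 1–5, cough days 20–22 | 2 (gap 14) | 2 (gap 14) |

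A lowers the count under the SAP rule, B and C raise it, and D leaves it unchanged. If blocked nose replaces runny nose in B, the result is again 1 against 2. The net direction therefore depends on the mix of illnesses, which the documents do not give.

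**The case against.** The best defence is that the sentence only separates episodes, while Table 12 decides what is a case. An infant with a nasal-only illness still meets the all-cause RTI definition, and a table of infants with at least one RTI would not need the episode rule. SAP section 5.4.1 promises summaries of occurrence without saying whether infants or episodes are counted, and the methods cells are redacted. This stands, and it limits the finding to tabulation by episode. It does not reconcile the two lists: the sentence is written for RTI episodes and is the only visible counting rule.

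A second defence is that runny nose may have been left out on purpose, because Protocol section 8.4.6 sets it aside as often chronic. That is plausible, but the SAP does not say so and the exemption does not extend to blocked nose.

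Third, the reach is small. Infant RTI is not a primary or secondary efficacy endpoint in SAP Table 1, and SAP section 8 calls the vaccine-efficacy endpoints descriptive. RSV-RTI is probably touched less than all-cause RTI. Swabs come from assessment visits or RTI hospitalisation (Protocol Table 14), and the visits are triggered by breathing difficulty, wheezing, or parental concern with intent to seek care (Protocol section 8.4.3.2). All of this stands.

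A reader might go further and infer that the gap wording inflates LRTI occurrences: read with *or*, an infant who stops coughing but still has difficulty in breathing would satisfy the gap and could start a second episode of one illness. The natural reading is a week free of both symptoms. The visible Kaplan-Meier analysis of time to RSV-LRTI (SAP section 5.2.1.1) would not ordinarily depend on a second episode, and the primary method is redacted. The wording deserves tightening, but it is not evidence of inflated LRTI counts.

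**Conclusion.** The rule is wrong as written for RTI, at low severity. It fits LRTI and contradicts Table 12's RTI definition on 4 of 15 symptom combinations. Where RSV-RTI or all-cause RTI is summarised by episode, nasal-only illnesses contribute nothing, breathing difficulty alone contributes an episode outside the definition, and one illness can be counted twice.

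The conclusion assumes that the sentence is applied literally and that at least some RTI summaries count episodes; the visible text does not settle the second point.

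Two stronger conclusions are not supported. One is that RTI episodes will certainly be understated by the share of nasal-only illnesses: no such share is given, and the timelines show errors in both directions. The other is that the primary endpoints, such as "From birth to 6 months, occurrences of any medically assessed, RSV-associated LRTIs according to the case definitions", are affected: their entry symptoms coincide with the rule on all 15 combinations.

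**What to change.** Replace the sentence in SAP section 9.2.2 with two rules and name the outputs each one serves.
- **LRTI episodes:** keep cough or difficulty in breathing as the opening symptoms, and require at least 7 consecutive days with neither before a new episode.
- **RTI summaries:** open an episode at new onset of a Table 12 RTI symptom after at least 7 consecutive days free of cough, blocked nose and difficulty in breathing. A continuing runny nose neither prolongs nor reopens an episode, in line with Protocol section 8.4.6.

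On the timelines above, the RTI rule gives 2 for A, 1 for C and 2 for D. B stays at 2, a deliberate result of not letting runny nose bridge the gap; with blocked nose in its place the count is 1. The SAP should also say what distinguishes a newly started runny nose from a continuing one, whether the RTI tables count infants or episodes, and whether either rule applies to maternal MA-RTI.

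The cost is two sentences and a small derivation change. Protocol Table 2 has only applicable diary data transcribed to the eCRF, so first confirm that start and end dates for nasal symptoms are in the database. The change would come after unblinding and after the 6-month interim analysis described in SAP section 7.1. Record it in SAP section 8 as a documented change, and check the 6-month RTI outputs for the reading used, so that interim and final tables agree or the difference is explained.
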